Occurrence of 1 st chemotherapy discontinuation during one-year follow-up period	Time to event	Incidence Rate on (0, 365d)	IRD and IRR	All MO
Occurrence of 1 st admission during one-year follow-up period	Time to event	Incidence Rate on (0, 365d)	IRD and IRR	All MO
Occurrence of 1 st re-operation during one-year follow-up period	Time to event	Incidence Rate on (0, 365d)	IRD and IRR	All Surg
Occurrence of 1 st re-admission during one-year follow-up period	Time to event	Incidence Rate on (0, 365d)	IRD and IRR	All Surg
Death during one-year follow-up period	Time to event	Incidence Rate on (0, 365d)	IRD and IRR	MO and Surg
Composite of EDTR, Hospitalization, and Death event occurrence status at Day 30	Binary	Proportion	Absolute Difference (AD) and Odds Ratio (OR)	MO and Surg
Death during 30-day post-chemotherapy start date (for MO) or at 30-day post-surgical discharge date (for Surg)	Time to event	Incidence Rate on (0, 30d)	IRD and IRR	MO and Surg
Notes:				

 The Day 1 is defined the chemotherapy start date for MO and the discharge date for Surgery. All outcomes are defined in relation to the date of discharge from hospital (for Surg) or the initiation date of a new chemotherapy regimen (for MO). Note that events occurring on the first day of chemotherapy or the day of discharge after surgery will be excluded, because they could not have been impacted by the eSym program. 				

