4.4. Multilevel Generalized Linear Regression Analysis

The primary analysis for the outcomes in Aim 2 (Table 5) will be performed via multilevel generalized linear regression models (or generalized linear mixed-effects model; GLMM).⁹ The null hypothesis for the statistical test is no intervention effect on the outcome, which indicates that the regression coefficient for the intervention indicator variable is zero. The intervention effect will be summarized in both absolute and relative terms (CONSORT Checklist Item 17b).⁷

Followings are specifications of the GLMM for the primary and secondary analyses.

- Link function
 - For binary outcomes, the logit-link will be used.
 - For count outcomes, the log-link will be used, and the follow-up time will be included as the offset in the model. (Poisson regression)
 - For time-to-event outcomes, we will use Poisson regression models, where the log-link will be used. The event indicator (1: event, 0: censoring) will be the response variable. Exposure time (i.e., days from the start date of the follow-up to either the date of the event occurrence or the end of follow-up, whichever comes first) will be included as the offset in the model.
- Treatment effect metrics
 - Following the recommendation of the CONSORT guideline,⁷ we will report the treatment effect in both absolute and relative metrics.
 - For binary outcomes, we will report odds ratio (OR) derived from the GLMM with the logit-link. In addition, we will calculate absolute difference (AD), using the resulting GLMM with G-computation. Bootstrap will be used to obtain a standard error for the estimated AD.
 - For count outcomes and time-to-event outcomes, we will report the incidence rate ratio (IRR) derived from the GLMM model. In addition, we will calculate absolute difference in incidence rate (i.e., incidence rate difference;IRD) in a similar way to calculate AD.
- Secular trend
 - Primary: Calendar time of the start date of the follow-up of each episode will be included as a continuous variable with natural cubic spline with 3 knots
 - Secondary: Period in which the trigger event occurs will be included as a categorical variable.
- Site (cluster)

- Since there are only 6 sites in this study, the conventional analysis of including cluster as random-effects is problematic due to this small number.¹⁰
- Primary: The primary analysis includes sites as fixed effects.

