5.3. Power Considerations

Our general approach is to determine the magnitude of difference detectable at a given sample size. Because we have insufficient preliminary information about the magnitude of the ICCs or standard deviations (SD) for our outcomes, we will consider a broad range.

For MO, assuming the average duration of chemotherapy is 180 days in the eSyM- group, the range of detectable between group differences is shown in **Table 11A**. Based on these very

conservative estimates, we have more than 80% power to detect a 16% increase in chemotherapy duration, which corresponds to nearly 1 month.

For Surg, we assume that the average duration from surgery to adjuvant chemotherapy start date (censored at 6 months) is 56 days (8 weeks) in the eSyM- group. With 1212 patients (see **Table 10**), and conservative parameter estimates, we have >80% power to detect a 25% increase in the interval between surgery and starting adjuvant therapy. This corresponds to 14 days, a difference that is both plausible and meaningful, see **Table 11B**.

Table 11: Power considerations for the outcomes of Aim 2b

A: MO 3024 patients (1512 per group)

Detectable effect size with 80% power	Assumed ICC	Assumed standard deviation [Day]	Difference in time to discontinuation	Corresponding ratio in the eSyM- group
0.138	0.01% (Very low)	202 (conservative)	28 days	1.16
		152	21 days	1.12
		101	14 days	1.08
0.170	1%	165 (conservative)	28 days	1.16
		124	21 days	1.12
		82	14 days	1.08
0.174	5% (conservative)	161 (conservative)	28 days	1.16
		120	21 days	1.12
		80	14 days	1.08

B: Surg 1212 patients (606 per group)

Detectable effect size with 80% power	Assumed ICC	Assumed standard deviation	Difference in time to adjuvant chemo	Corresponding ratio in eSyM- group
0.217	0.01% (Very low)	65 (conservative)	14 days	1.25
		32	7 days	1.13
0.256	1%	55 (conservative)	14 days	1.25
		27	7 days	1.13
0.271	5% (conservative)	52 (conservative)	14 days	1.25
		26	7 days	1.13

6. Analysis for Aim 2c: Patients' outcomes, indicated by levels of self-efficacy and symptom burden

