 - o The primary analysis will consider random intercepts only.

Revised:

- The primary analysis for the outcomes in Aim 2 (Table 5) will be performed via generalized linear regression models (or generalized linear model; GLIM).
- Subjects
 - o We will potentially have more than one episode from one subject in this study. However, only the 1st episode from each patient will be included in the primary analysis.
 - o If possible, as a sensitivity analysis, we will perform multilevel generalized linear regression models (or generalized linear mixed-effects model; GLMM) by including all episodes. To take account of within-subject correlation, subjects will be included as random effects.

5. Sensitivity analyses (Page 19):

Original:

- Analysis with data from the first episode
 - o In the primary analysis, all episodes in the analyses except for eSyM- episodes contaminated with the eSyM intervention will be included. We will perform sensitivity analyses using only the first episode from each patient. In these sensitivity analyses, each patient will serve only one data point in the analysis.

Revised:

- Analysis with data from all episodes
 - o In the primary analysis, only the first episode from each patient will be used. In the primary analysis, each patient will serve only one data point in the analysis. We will perform sensitivity analyses using all episodes in the analyses except for eSyM- episodes contaminated with the eSyM intervention will be included.

Implementation and Documentation

These changes will be implemented immediately and documented in all relevant study documents and communications. The SAP addendum will be reviewed and approved by the IRB. All analyses will be conducted based on this SAP addendum.

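### The IRR tests for the six time-to-event outcomes rest on a constant hazard because SAP 4.4 states no robust variance; type I error can fall near 0% or rise to about 13%, depending on the outcome.

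*SAP*

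**What the plan says.** Table 5 (SAP 4.1) lists six time-to-event outcomes. One is "Occurrence of 1 st chemotherapy discontinuation during one-year follow-up period". The others are first admission, first re-operation, first re-admission, death within one year and death within 30 days. Each is summarised as an incidence rate over the window, and conditions are compared by a rate difference (IRD) and a rate ratio (IRR).

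SAP 4.4 gives the model: "For time-to-event outcomes, we will use Poisson regression models, where the log-link will be used". It adds "The event indicator (1: event, 0: censoring) will be the response variable", with exposure time as the offset, so one rate covers the whole 30 or 365 days. Addendum change 4 restricts the primary analysis to first episodes, "will be performed via generalized linear regression models (or generalized linear model; GLIM").

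On variance, SAP 4.4 says of the absolute difference for binary outcomes: "Bootstrap will be used to obtain a standard error for the estimated AD". The IRD is the "absolute difference in incidence rate (i.e., incidence rate difference;IRD) in a similar way to calculate AD". Nothing comparable is said for the IRR. The null hypothesis in 4.4 is only that the intervention coefficient is zero.

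The only event-time figures in the documents are for chemotherapy duration. SAP 5.3 begins "For MO, assuming the average duration of chemotherapy is 180 days in the eSyM- group", and Table 11A pairs that mean with SDs from 80 to 202 days.

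**The concern.** A Poisson likelihood on a 0/1 event with a log-exposure offset is the exponential survival likelihood. Its model-based variance treats the number of events as the whole information. That is right when the hazard is constant over follow-up, which a null of no intervention effect does not imply.

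Chemotherapy courses may have fairly regular lengths, so that the hazard rises. The model-based standard error (SE) is then too large and real differences are missed. Admissions after discharge, or after starting chemotherapy, may cluster early, so that the hazard falls. The SE is then too small and an ineffective programme is declared to have an effect more often than 5% of the time. At stake are the IRR intervals and p-values for secondary outcomes, with errors that can run in opposite directions within one table.

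**Working it through.** **1. Reproduce the plan's figure.** Inputs: 6 sites, 7 periods, 72 patients per site-period (Table 3; N = 3,024 medical oncology patients), two-sided 5% (stated for Table 9, assumed for Table 11), 80% power, and steps at periods 2 to 7. The Hussey–Hughes variance in SD units, with s² = (1−ρ)/72 and τ² = ρ, is

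Var = I·s²(s² + Tτ²) / [(IU − W)s² + (U² + ITU − TW − IV)τ²].

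Here I = 6, T = 7, U = 21, W = 91 and V = 91, so IU − W = 35 and the last bracket is 441 + 882 − 637 − 546 = 140. For ρ = 0.0001, Var = 0.00243, SE = 0.0493 and 2.80 × SE = 0.138. For ρ = 1% and 5% the results are 0.170 and 0.174. All three match Table 11A.

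**2. Variance ratio.** Let D be the event indicator, T the time to event or day 365, and r = E[D]/E[T]. The model takes Var(D − rT) to be E[D]. Define

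R = Var(D − rT)/E[D] = (E[D] − 2r·E[DT] + r²·E[T²])/E[D], and true size = 2{1 − Φ(1.96/√R)}.

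R is 1 for an exponential. An exponential with a mean of 180 days restricted to 365 has an SD of about 127 days, so the test is conservative below that SD and anti-conservative above it (Weibull family).

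**3. Discontinuation.** Weibull times were matched to a restricted mean of 180 days and to Table 11A's SDs after truncation.

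- SD 80: E[D] = 0.980, r = 0.980/180 = 0.005445, E[DT] = 172.7, E[T²] = 80² + 180² = 38,800. R = (0.980 − 1.881 + 1.150)/0.980 = 0.25, so size = 0.01%.
- SD 161: E[D] = 0.624, r = 0.003469, E[DT] = 42.9, E[T²] = 58,321. R = (0.624 − 0.298 + 0.702)/0.624 = 1.65, so size = 12.7%.

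Simulation on the same 6 × 7 × 72 layout (fixed site and period, 1,500 trials per cell) compares the model SE with a patient-level sandwich SE:

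| SD (days) | R | Size by formula | Simulated size, model / sandwich | Difference | Power, model / sandwich |
|---|---|---|---|---|---|
| 80 | 0.25 | 0.01% | 0% / 4.3% | +14 d | 14% / 78% |
| 101 | 0.53 | 0.7% | 0.9% / 4.7% | +14 d | 34% / 61% |
| 120 | 0.86 | 3.5% | 2.5% / 4.4% | +21 d | 77% / 81% |
| 152 | 1.48 | 10.7% | 9.5% / 3.9% | +21 d | 72% / 61% |
| 161 | 1.65 | 12.7% | 13.1% / 4.9% | +28 d | 88% / 79% |

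In the last two rows the model's apparent extra power comes from its inflated size.

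The result depends on how Table 11A's SD is read. With gamma durations whose SD applies before truncation, +14 days at SD 80 gives 10–12% against 68–74%, and +28 days gives 87–91% against 100%. At SD 120 the figures for +14 days are 17% against 39%, and at SD 161 they are 18% against 24%. The SD of 202 cannot be matched after truncation: the largest SD possible on 0–365 with mean 180 is √(180 × 185) = 182.5.

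**4. Front-loaded outcomes.** The documents give neither incidence nor hazard shape, so both are assumed.

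| One-year risk | Size, Weibull shape 0.5 | Size, Weibull shape 0.3 |
|---|---|---|
| 20% | 5.9% | 6.5% |
| 40% | 7.3% | 8.9% |

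At shape 0.5 and 50% risk, size is 8.3%. Simulated sizes at 20–40% risk (shapes 0.3–0.7) were 6.1–8.2% with the model SE and 3.9–5.4% with the sandwich.

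**5. Rare outcomes.** If all events fell at time zero, R would reach its ceiling of 1/(1 − p). At p = 5% that is 1.053, a size of 5.6%. At 1–2% the ceiling size is 5.1–5.2%.

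**The case against.** The strongest reply is that little depends on this. The primary outcome is binary EDTR at Day 30. All six outcomes are secondary, and none appears in the results shell of SAP 4.8. Aim 2b already analyses chemotherapy start-to-stop days as a mean difference, and Table 11A powers that analysis, not the Table 5 row. The documents do not say that Table 5's discontinuation is the same event as Aim 2b's regimen stop, so applying Table 11A's mean and SDs to it is an assumption. The IRD follows the bootstrap route. Early hospital use is also tested by binary Day 30 and Day 90 outcomes. All of this stands and limits the consequence. It does not repair the IRR intervals and p-values.

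A reader might infer three stronger things.

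- That discontinuation loses most of its power. This holds only for the smallest difference in Table 11A and SDs near 80–100. SAP 5.3's benchmark is nearly a month, and at SD 80 the power for +28 days is 87–91%. At SDs of 152–161 matched after truncation the error reverses.
- That all six outcomes are affected alike. Rare ones are hardly touched.
- That the IRR itself is wrong. Table 5 targets an incidence rate over the window, and a ratio of average rates is meaningful without a constant hazard. Falling short of a hazard ratio is no fault, since the SAP does not target one.

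**Conclusion.** The point holds for the model-based interval and p-value of the IRR. Under the model as written, the discontinuation test runs from near 0% to roughly 10–13% type I error across Table 11A's SDs of 80–161 days. SAP 5.3 says preliminary information on the SDs is insufficient, so the direction cannot be known in advance. For common, early-clustering outcomes the inflation is moderate, about 6–9%. For 30-day death it is negligible, as it is for re-operation if that is rare.

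These figures assume gamma or Weibull times, no censoring before day 365, equal cells at the minimum sample size, and seven periods without the added Period 8. The (re)admission figures also rest on assumed risks and shapes. This is more than a missing detail, because the stated model run with default errors gives wrong error bars. It does not threaten the trial's main conclusion.

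**What to change.** In SAP 4.4, under time-to-event outcomes, state that the IRR's confidence interval and p-value use a robust (sandwich) SE computed at patient level, with sites kept as fixed effects. Alternatively, extend to the IRR the bootstrap already planned for the absolute measures. Either keeps Table 5's incidence-rate estimand. In the simulations of discontinuation and front-loaded outcomes on the 6 × 7 × 72 layout, the sandwich brought size to 3.9–5.4%.

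Optionally, add a piecewise-exponential Poisson or Cox model as a sensitivity analysis, noting that it estimates a hazard-type ratio and not the one-year average rate ratio. It should not replace the planned summary.

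The cost is one sentence in the SAP and a few lines of code, with no new data.

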### **Activity 3b: User Acceptability Testing (UAT)**

**Informed Consent: Waiver of documentation of consent.** Before observing the patient using eSyM, the patient will be provided with a letter (see appendix O) with the elements of informed consent, as well as the option not to be observed. They will be notified that participation is completely voluntary and can be stopped at any time for any reason. This activity is minimal risk.

**Methods that will be used to identify potential subjects:** Under a HIPAA waiver, study staff will look in the scheduling views of the electronic medical record and scheduling systems to identify potential participants. Study staff may also query Epic, administrative/operations/billing databases, order entry databases, and/or cancer registry databases to identify potential participants. Study staff may also accept potential patient referrals from site clinicians. Purposive sampling based on data from the electronic medical record (e.g., demographics, cancer stage, number of recent hospitalizations, number of prescription drugs) will be used to ensure that perspectives of diverse patients are included. Ideally, sites will use the developed eSyM reporting workbench reports in Epic to automatically pull a patient list for UAT.

**When, where, and how potential subjects will be recruited:** The clinical/study staff will approach the patient to see if they would be interested in participating in UAT. If a patient is interested in participating, the site will present the participant with a study letter and then begin observations. Patients may be approached in-person, via phone, via email or through a virtual visit.

**Description of procedures being performed for UAT:** Surgical patients will be set up to use eSyM at the time of surgical discharge (or at the site's discretion). Medical oncology patients will be set up to use eSyM at the time of their first chemotherapy dose visit (or at the site's discretion). The study staff will observe the patient accessing eSyM, the patient being trained on how to use eSyM, the patient using eSyM to do their first symptom reporting session.

**Duration of subject's participation in the study:** Per protocol, UAT observation will last approximately 30 minutes or less.

**What data will be collected and how:** The study staff will write down their observations as well as staff/patient feedback (see appendix P).

**Study design:** User acceptability testing.

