To develop clinical risk scores, we will select approximately 20 independent variables that can be easily abstracted from a patient's medical chart, such as diagnosis, treatment, comorbid conditions, recent hospitalizations, and demographics. Within the training cohort, we plan to use logistic regression with L1 regularization to select variables for inclusion and define the prediction model. The amount of regularization will be tuned using the validation cohort and models will be iteratively trained until a final candidate model is identified. Like above, these steps will be completed separately for the ePRO-responding and total cohorts. The area under the receiver operator characteristic curve (AUC-ROC) will be used to compare the performance (i.e., predictive ability) of different models.

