- 3) As exploratory analyses, we will compare A vs. B. Under the condition that the hospitals have switched on the eSyM system (i.e., everybody is exposed to the eSyM system), we are interested in estimating the effect of the eSyM engagement on the outcomes under the assumption that everyone engages with eSyM, compared to the case where no one engaged with eSyM in spite of eSyM exposure. A propensity score weighting will be used to adjust for the case-mix between engagement with eSyM and non-engagmenet with eSyM. We will build a propensity score model for MO and Surg, separately, using the data from A and B. The pre-specified variables used for the propensity score models are listed in **Table 7**. No outcome model will be involved in this analysis.

Table 7: Pre-specified variables included in the propensity score models

Variable	2) A vs. C*	3) A vs. B	Note
Goal of Chemotherapy (MO with curative goal, MO with palliative goal, Others)	X	X	Only the models for MO
Calendar Time (Secular trends) [continuous with natural cubic spline]		X	
Site (Treating Facility) (DFCI, MMC, DHMC, LCI, BAPT, WVU)	X	X	
Age (year) (fractional polynomials)	X	X	
Sex (male vs. female)	X	X	
Race/Ethnicity (white/non-Hispanic, black/non-Hispanic, Hispanic, Other/Unknown)	X	X	
Employment (Employed, disabled, retired, other)	X	X	
Marital status (married vs. not married)	X	X	
Rurality based on zip code (large metro, small metro, suburban, rural)	X	X	
Insurance type (Medicare only, Medicare and Medicaid, Medicaid only, Private, Other)	X	X	
Cancer type (GI, Gyn, Thoracic)	X	X	
Socio-economic status (quintiles by the zip code-based poverty level)	X	X	
Co-morbidity (Charlson comorbidity index from encounter diagnoses in the 12 months before the first eligibility date) (0, 1, 2+)	X	X	

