- Secondary: Sites will be included as random-effects with a small sample adjustment (the Kenward-Roger method).^{11,12}
- Subjects
 - We will potentially have more than one data point from one subject in this study.
 - To take account of within-subject correlation, subjects will be included as random effects.
 - The primary analysis will consider random intercepts only.
- Variables to be included the GLMM
 - **Table 8** lists the variables selected based on the study design (Category A) and clinical importance (Category B and C).
 - The primary analysis includes the variables in Category A and B.
 - As a secondary analysis, we will perform the same analysis including Category A, B and C.

Table 8: Variables that will or may be included in the generalized linear mixed-effects model for the primary analysis

Variable	Category A	Category B	Category C
Intervention indicator: (eSyM+ vs. eSyM-)	X		
Cohort (MO vs. Surgery)	X		
Calendar Time (Secular trends) [continuous with natural cubic spline]	X		
Site (Treating Facility) (DFCI, MMC, DHMC, LCI, BAPT, WVU) [as fixed effects]	X		
Interaction between Cohort (MO vs. Surgery) and Calendar Time (Secular trends)	X		
Interaction between Cohort (MO vs. Surgery) Site (Treating Facility) (DFCI, MMC, DHMC, LCI, BAPT, WVU) [as fixed effects]	X		
Subjects [as random effects (random intercepts only)]	X		
Goal of Chemotherapy (MO with curative goal, MO with palliative goal, Others)		X	
Age (years) (fractional polynomials)		X	
Sex (male vs. female)		X	
Race/Ethnicity (white/non-Hispanic, black/non-Hispanic, Hispanic, Other/Unknown)		X	
Rurality based on zip code (large metro, small metro, suburban, rural)		X	
Cancer/procedure type (GI, Gyn, Thoracic)		X	
Employment (Employed, Disabled, Retired, Other)			X
Marital status (Married vs. Not married)			X
Insurance type (Medicare only, Medicare and Medicaid, Medicaid only, Private, Other)			X
Socio-economic status (quintiles by the zip code-based poverty level)			X
Co-morbidity (Charlson comorbidity index from encounter diagnoses in the 12 months before the first eligibility date) (0, 1, 2+)			X

- Time decay of the intervention effect

- As a sensitivity analysis, we will include the interaction between the intervention and time from the rollout of the intervention condition at the treating site to the time of the trigger event, where we treat the time as a categorical variable in the model.

Considerations on the potential informative censoring

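### Prior ED and hospital use is missing from the outcome models and both propensity models; this matters most for the engagement comparisons (A v C* and A v B)

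*SAP*

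**What the plan says.** SAP 4.4 sorts the covariates in Table 8 into three categories. "The primary analysis includes the variables in Category A and B", and "As a secondary analysis, we will perform the same analysis including Category A, B and C". Category B holds chemotherapy goal, age, sex, race/ethnicity, rurality and organ site. The Charlson index, "Charlson comorbidity index from encounter diagnoses in the 12 months before the first eligibility date", is in Category C. The chemotherapy-goal row reads "Goal of Chemotherapy (MO with curative goal, MO with palliative goal, Others"), so a surgical patient can only fall in the last level.

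Table 7 (SAP 4.2) lists the propensity-score variables for A v C* (engaged patients against matched controls) and A v B (engaged against non-engaged). It marks the Charlson index for both. Only chemotherapy goal carries a restriction: "Only the models for MO". Matched A v C* data then go through the primary outcome model. A v B uses propensity weighting with no outcome model.

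The June 2024 Addendum moves the primary analysis to first episodes and to a generalized linear model. It leaves the variable lists in Tables 7 and 8 unchanged.

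**The concern.** A patient's recent ED visits and admissions are the natural baseline measure for an outcome that is itself an ED visit. The protocol treats them that way elsewhere. The Activity 5 risk scores, for the same kind of outcome, draw on chart variables "such as diagnosis, treatment, comorbid conditions, recent hospitalizations, and demographics".

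The gap bears on two kinds of comparison.

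- **Engagement comparisons.** Engagement means at least one symptom report during follow-up, so patients choose it. If recent acute-care use is related both to reporting and to later ED visits, the propensity score leaves that confounding in place. In A v B nothing else can remove it. In A v C* the outcome model that follows matching lacks the same variable.
- **Primary comparison.** SAP 4.7 supports its low intracluster correlation partly by saying that regression adjustment for baseline risk will make case-mix differences between sites negligible. For surgical patients that adjustment rests on demographics and organ site. SAP 3.6 reports that COVID left ED events below expectation at three sites, so case-mix change that differs by site is a reasonable worry.

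**Working it through.** The plan states no figure on this point. The check is a reading of the covariate lists, followed by an illustration of size.

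**1. What each model contains**

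| Variable | Primary (A+B) | Secondary (A+B+C) | Propensity, A v C* | Propensity, A v B |
|---|---|---|---|---|
| Prior ED or hospital use | no | no | no | no |
| Charlson index | no | yes | yes | yes |
| Stage, procedure extent | no | no | no | no |
| Chemotherapy goal | yes (no surgical levels) | yes (no surgical levels) | MO only | MO only |
| Organ site | yes | yes | yes | yes |

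**2. Whether the data exist**

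- The Charlson index already reads encounters from the 12 months before first eligibility.
- Activity 5 uses only data collected in Activity 4. It lists inpatient and outpatient encounters among them and names recent hospitalizations as an input.
- The Activity 4c list (Protocol 12.0) includes ED visits and admissions with dates, but as outcomes. No pre-index ED field is named.

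Availability is therefore a well-supported inference that still has to be confirmed.

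**3. Possible bias in the absolute difference**

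Bias = residual imbalance in prior use × risk difference in the outcome between patients with and without prior use.

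From SAP 4.7: a control rate of 8% to 15% and a hypothesised effect of 3 to 4 points. Assumed, not in the documents: 15% to 25% of patients with prior use, and an odds ratio of 2 to 4 with the outcome. Solving for the risk difference across these inputs gives 5.75 points (rate 8%, prevalence 25%, odds ratio 2) to 22.8 points (rate 15%, prevalence 15%, odds ratio 4).

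| Residual imbalance (assumed) | Bias, points | Share of a 3-point effect |
|---|---|---|
| 2 points | 0.12 to 0.46 | 4% to 15% |
| 5 points | 0.29 to 1.14 | 10% to 38% |
| 10 points | 0.58 to 2.28 | 19% to 76% |

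A simple case inside this range: risks of 18% and 8% with a 5-point imbalance give 0.05 × 10 = 0.5 point. The direction is unknown, because the documents do not say how prior use relates to engagement.

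**4. Possible gain in precision**

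Share of outcome variance explained = q(1−q)(r1−r0)² / [p(1−p)], with r1 = 18%, r0 = 8% and p = 10% (all assumed):

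- q = 0.15: 0.1275 × 0.01 / 0.09 = 1.4%
- q = 0.20: 0.16 × 0.01 / 0.09 = 1.8%
- q = 0.25: 0.1875 × 0.01 / 0.09 = 2.1%

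On 6,048 patients, 1.4% to 2.1% is about 85 to 125 patients. This is an upper figure, because age, organ site and chemotherapy goal already explain part of the same variance.

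**The case against.** The strongest reply is that the primary comparison is already well protected. Go-live was staggered and randomised. Site and cohort-by-site fixed effects remove stable differences between sites, and the cohort-specific calendar-time spline removes trends shared by all sites. SAP 4.6 adds a sensitivity analysis with site-specific COVID prevalence. This stands. There is no site-by-time term, so site-specific drift aligned with go-live is not absorbed, but only that part remains. The bias formula takes residual imbalance. A raw before-after difference in prior use caused by a common trend would leave almost none, so a reader should not take 0.5 point as the bias of the primary estimate.

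Two other stronger readings are tempting and are not supported.

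- A reader might infer that surgical patients have no severity covariate anywhere. Table 7 gives them the Charlson index in both propensity models; what those models lack is prior use, stage and procedure extent.
- A reader might infer that the outcome is never adjusted for comorbidity. The A+B+C secondary analysis does this.

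Two further points against a change also stand. First, the Addendum reports convergence failures, so modelling had begun by June 2024, and altering primary covariates then is more than a wording change. Second, a 12-month window before each Day 1 would, in the all-episodes sensitivity analysis, adjust later intervention episodes for ED use that followed eSyM exposure.

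On availability, Activity 3b does let site staff sample on record data ("demographics, cancer stage, number of recent hospitalizations, number of prescription drugs"), but that concerns usability testing and says nothing about the trial extract.

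**Conclusion.** The omission is real and worth correcting, chiefly in the propensity models. Prior ED or hospital use is in none of the four covariate sets, and the primary model gives surgical patients no comorbidity, stage or procedure-extent term.

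For A v C* and A v B, the imbalances that self-selection can produce are large enough to matter: at 5 points, about 0.3 to 1.1 points of bias. These analyses are secondary and exploratory respectively.

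For the primary comparison, the low end of the bias table is the more plausible, and the precision gain of at most about 1-2% would not by itself justify a change. The documents do not support a claim that the primary result is materially biased.

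All sizes rest on assumed prevalence, odds ratio and imbalance. The reading of the tables does not.

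**What to change.** 1. Confirm that pre-index ED encounters are in the extract. Then derive one variable: any ED visit or unplanned hospital admission in the 12 months before the first eligibility date, counted before the index admission for Surg. State how planned admissions are identified; the Activity 5 exclusion rule is a starting point.
2. Add it to both columns of Table 7.
3. If outcome results by condition have not been seen, add it and the Charlson index to Category B of Table 8. If they have been seen, leave the primary model as it is, and report that model plus these two covariates as a labelled sensitivity analysis.
4. Record in the SAP which of these two situations applies.

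The cost is one derived variable and SAP wording. There are small downsides: care outside the health system may be missed, and COVID may itself have lowered prior use in part of the study period. Anchoring at first eligibility, as the Charlson index already is, avoids adjusting later episodes for ED use after exposure.
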